6.2 Exclusion (Eligibility) Criteria

Subjects meeting any of the following criteria will be excluded from the study:

1. History of significant sensitivity or allergy to androgens, castor oil or product excipients.
2. Clinically significant findings in the pre-study examinations including abnormal breast examination requiring follow-up.

3. Abnormal prostate digital rectal examination (DRE) with palpable nodule(s) or I-PSS score > 19 points.
4. Body mass index (BMI) ≥ 35 kg/m².
5. Azoospermia or severe oligospermia (<1 million sperm/cc) on screening semen analysis: no sperm found in direct nor centrifuged semen sample or previous history of vasectomy.
6. Clinically significant abnormal laboratory value, in the opinion of the investigator, in serum chemistry, hematology, or urinalysis including but not limited to:
 - a. Baseline hemoglobin > 16 g/dL
 - b. Hematocrit < 35% or > 50%
 - c. PSA > 4 ng/mL and age >40
7. History of seizures or convulsions, including febrile, alcohol or drug withdrawal seizures.
8. History of any clinically significant illness, infection, or surgical procedure within 4 weeks prior to study drug administration.
9. History of stroke or myocardial infarction within the past 5 years.
10. History of, or current or suspected, prostate or breast cancer.
11. History of diagnosed, severe, untreated, obstructive sleep apnea.
12. History of abuse of alcohol or any drug substance in the opinion of the investigator within the previous 2 years.
13. History of nasal disorders such as nasal polyps; nasal septal perforation; nasal surgery; nasal trauma resulting in nasal fracture within the previous 6 months or nasal fracture that caused a deviated anterior nasal septum; sinus surgery or sinus disease
14. Donation or loss of 550 mL or more blood volume (including plasmapheresis) or receipt of a transfusion of any blood product within 12 weeks prior to the start of treatment.
15. Inadequate venous access for collection of serial blood samples required for pharmacokinetic profiles.
16. Receipt of any investigational product within 4 weeks or within 5 half-lives prior to the start of treatment.

17. Inability to understand and provide written informed consent for the study.
18. Considered by the investigator or the sponsor-designated physician, for any reason, that the subject is an unsuitable candidate to receive Natesto.
19. History of treatment with clomiphene citrate within the last 12 months.
20. History of varicocele repair.
21. Actively seeking conception unless agreeing on sperm cryopreservation for a minimum of 12 months from enrollment in the study.

6.3 Study Population

The study will consist of 80 males suffering from idiopathic hypogonadism.

6.4 Setting

Subjects will be identified from those visiting the University of Miami – Department of Urology and the UHealth Fertility Center, and receiving the diagnosis of idiopathic hypogonadism. If they meet the inclusion criteria, the patients will receive an explanation of the study. Patients will be informed both verbally and in written form of the study and procedures involved. The PI, Resident, Fellows and/or the study coordinator will obtain a signed/dated Informed Consent Document (ICD) before enrolling each subject. Subsequent visits will take place in the same Clinic. Study data will be safely stored in a RedCap database.

7. STUDY DESIGN, CLINICAL, RADIOLOGICAL, LABORATORY AND SURGICAL EVALUATIONS

7.1 Study Design

This is a prospective clinical study aimed to evaluate the safety and efficacy of Natesto TM on patients with idiopathic hypogonadism. Clinical signs and symptoms of hypogonadism, i.e. diminished energy and sexual function; and/or a decreased sperm count constitute the clinical indication for TRT in our study population.

7.2 Screening Evaluations and Procedures

The first visit of the patients will be for screening and medical evaluation. Patient's medical co-medication history will be collected and documented and a physical examination will be performed.

Previous month's blood test results will be reviewed including a general chemistry panel, a lipid profile, and Testosterone levels during chart review.

Patients will sign an informed consent and in case they meet all inclusion criteria (and do not meet any exclusion criteria), they will be recruited to the study.

7.3 Pre-Treatment Procedures and Evaluations

Upon evaluating the inclusion/exclusion criteria, patients will be recruited to the study. Patients will be instructed to stop any use of androgen replacement for 4 weeks prior to first treatment session and refrain from using any other androgen replacement therapy option during the study. After the washout period and before the first treatment session, patients will answer the IIEF-EF and SF-36 questionnaires for baseline evaluation.

7.4 Follow-Up Procedures and Evaluations:

Follow-up visits will be conducted at week 14+/- 7 days and 26+/- 7 days, these visits shall include:

- Measuring IIEF-EF and SF-36 scores of patients at the clinic
- Taking serum FSH, LH, E, and total Testosterone levels
- Semen analysis
- Reporting and recording adverse events at every follow-up visit.

Additional determinations of total serum testosterone will be performed periodically at every follow up visit, beginning one month after initiation of therapy. Additional semen analysis will be performed at weeks 15+/- 7 days and 27+/- 7 days.

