6. PATIENT SELECTION/ELIGIBILITY CRITERIA

6.1 Inclusion (Eligibility) Criteria

Subjects must meet the following criteria:

1. Voluntarily sign and date the study consent form(s) which have been approved by an Institutional Review Board (IRB). Written consent must be obtained prior to the initiation of any study procedures.
2. Male between 18 and 55 years of age, inclusive, with documented onset of hypogonadism prior to age 55.
3. Documented diagnosis of primary hypogonadism (congenital or acquired) or hypogonadotropic hypogonadism (congenital or acquired).
4. Serum total testosterone < 350 ng/dL based on 2 consecutive blood samples obtained 1-4 weeks apart between 6 and 10 AM following an appropriate washout of current androgen replacement therapy; with clinical symptoms of hypogonadism such as diminished energy and sexual function; and/or a decreased sperm count (<20 million sperm/mL semen).
5. Naïve to androgen replacement or has discontinued current treatment and completed a washout of 4 weeks following androgen treatment (excluding Testopel TM). Washout must be completed prior to collection of baseline serum testosterone samples to determine study eligibility.
6. Judged to be in good general health as determined by the principal investigator based upon the results of a medical history, physical examination, vital signs, and laboratory profile and a 12-lead electrocardiogram (ECG) performed at the time of enrolment of within the previous 6 months.

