12. STUDY CALENDAR

| Visit #, Time | Visit 1 (Week 1) Screening | Visit 2 (Week 2) | Visit 3 (Week 6) | Visit 4 (Week 14) | Visit 5 (Week 15) | Visit 6 (Week 26) | Visit 7 (Week 27) |
|--------------------------------------|-------------------------------|---------------------|---------------------|----------------------|----------------------|----------------------|----------------------|
| Medical & Urological History | • | | | | | | |
| Physical Examination & Questionnaire | • | | | • | | • | |
| Informed Consent | • | | | | | | |
| Inclusion & Exclusion Criteria | • | | | | | | |
| Blood Analysis (FSH, LH, T, E) | • | | • (Only T) | • | • (Only T) | • | • (Only T) |
| Semen Analysis | • | • | | • | • | • | • |
| Drug dispensing | | • | | • | | | |

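### For men still on androgens at Visit 1, the calendar allows 1 week for pre-dose steps that need 5 to 8, and takes its only baseline FSH, LH and estrogen before washout

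*Combined protocol and SAP*

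**What the plan says.** All references are to the combined protocol and SAP.

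- **Section 7.3** deals with men already recruited: "Patients will be instructed to stop any use of androgen replacement for 4 weeks prior to first treatment session". It then places the questionnaires: "After the washout period and before the first treatment session, patients will answer the IIEF-EF and SF-36 questionnaires for baseline evaluation".
- **Section 6.1, item 1**: "Written consent must be obtained prior to the initiation of any study procedures".
- **Section 6.1, item 4**: "Serum total testosterone < 350 ng/dL based on 2 consecutive blood samples obtained 1-4 weeks apart", following washout.
- **Section 6.1, item 5**: a man must be naive to androgens or have finished a 4-week washout, and "Washout must be completed prior to collection of baseline serum testosterone samples to determine study eligibility".
- **Section 12 (calendar)**: consent and the eligibility check fall at "Visit 1 (Week 1) Screening". Drug is first dispensed at Visit 2, in Week 2. The hormone row ("Blood Analysis (FSH, LH, T, E") has one pre-dose mark, at Visit 1. The row "Physical Examination & Questionnaire" also has one pre-dose mark, at Visit 1. Semen has two, at Visits 1 and 2. No washout interval and no second pre-dose testosterone sample appear.
- **Section 3.1** makes change from baseline in LH, FSH, testosterone, estrogen and quality of life the primary outcomes. Section 3.2 makes change in sperm count secondary, while section 10.1 lists semen analysis with the primary endpoints.

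**The concern.** The eligibility rules and section 7.3 describe one order of events, and the calendar describes another. For a man who arrives on androgen replacement, both cannot be followed.

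If the site follows the calendar, his baseline FSH, LH and estrogen are measured while he is on his earlier product. The later values are measured on Natesto. The difference then combines the effect of stopping one androgen with the effect of starting another, and nothing in the schedule separates them. The study is uncontrolled and section 10.4 analyses hormones with one-sample methods, so a contaminated baseline goes straight into the estimate.

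The same applies to sperm count where the scheduled semen samples serve as baseline. Section 1.3 itself reports that topical testosterone gel markedly reduces spermatogenesis, so a sample given on such a product is not a clean starting point.

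**Working it through.** **Check of the calendar against the plan's own figures.** Time on drug is calendar week minus the dispensing week (2).

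| Calendar week | 6 | 14 | 15 | 26 | 27 |
|---|---|---|---|---|---|
| Weeks from first dispensing | 4 | 12 | 13 | 24 | 25 |

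The value 26 − 2 = 24 reproduces the 24-week course in section 4.2. The value 6 − 2 = 4 reproduces the first testosterone check one month into therapy in section 7.4. The calendar therefore counts from screening, with drug starting in Week 2.

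**Time needed before the first dose, for a man on androgens at Visit 1.**

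1. Consent is a Visit 1 item and must precede study procedures (section 6.1, item 1). A washout instructed by the study therefore starts at Visit 1 at the earliest.
2. Washout: 4 weeks (sections 6.1 and 7.3).
3. Two testosterone samples after washout, 1 to 4 weeks apart (section 6.1, items 4 and 5).
4. Minimum: 4 + 1 = 5 weeks. With the widest spacing: 4 + 4 = 8 weeks. Both figures take the first sample on the day washout ends and allow no time for laboratory results.

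**Time available.** Week 2 − Week 1 = 1 week. The shortfall is 5 − 1 = 4 to 8 − 1 = 7 weeks. Against the washout alone it is 4 − 1 = 3 weeks.

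**Does a looser reading of the week labels help?** If each label covers a whole calendar week, the longest gap from Visit 1 to Visit 2 is 14 − 1 = 13 days. If both visits had a ±7-day window, which the documents do not give them, it is 7 + 14 = 21 days. Both are below the 28 days of washout.

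**Where the calendar's baseline measures fall, with washout starting at Visit 1.**

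| Measure | Pre-dose slot | Washout elapsed |
|---|---|---|
| FSH, LH, estrogen | Visit 1 only | 0 of 4 weeks |
| First semen sample | Visit 1 | 0 of 4 weeks |
| Second semen sample | Visit 2 | about 1 of 4 weeks |
| Questionnaires | Visit 1 only (section 7.3 says after washout) | 0 of 4 weeks |

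Testosterone is less exposed, because the eligibility samples supply a post-washout value. Nothing in the documents supplies a post-washout FSH, LH or estrogen. Even if the site held Visit 2 back until washout was complete, the calendar would still place those three at Visit 1.

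**The case against.** The strongest reply is that item 5 of section 6.1, read strictly, makes a man on androgens ineligible until he is washed out. Section 7.2 recruits only men who meet every criterion and reviews blood results from the previous month, so some work-up can precede Visit 1. On that reading the 1-week schedule is written for men who already qualify, and the affected group may be very small or empty. Much of this stands: naive men and men already washed out are unaffected, and nothing shows that anyone would be dosed in Week 2 on an on-androgen baseline. But section 7.3 gives its instruction to stop androgens after recruitment, so the plan foresees such men. If they are ineligible at Visit 1, their Visit 1 measures must be repeated, and the calendar has no slot for that. A chart testosterone taken on androgens fails item 5, and section 7.2's list of reviewed tests names no FSH, LH or estrogen.

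A second reply concerns quality of life. Section 7.3 expressly puts the baseline questionnaires after washout. That stands in full: here the calendar merely fails to match a clear instruction, and no bias claim follows.

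Three stronger readings are tempting:

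- A reader might infer that the LH and FSH results are biased towards no change, because an earlier androgen would lower the baseline. That is plausible, but the documents give neither the number of such men nor their hormone levels.
- A reader might infer from section 3.2, which counts 14 and 26 weeks from treatment, that exposure falls 2 weeks short. Sections 4.2, 7.4 and 12 agree on 12 and 24 weeks on drug, so this is probably a labelling slip. No sample size or analysis depends on it.
- A reader might infer that the Week 27 samples are taken off drug. Section 4.2 describes supply both as lasting for the study and as a 24-week course, so this is unclear. No consequence can be shown, and no change to supply is proposed.

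**Conclusion.** The point holds for men still on androgen replacement at Visit 1, and for them only. The steps required before dosing take 5 to 8 weeks and the calendar gives 1. Following it yields an on-androgen baseline for FSH, LH and estrogen, all primary change-from-baseline outcomes in section 3.1. It also yields semen baselines taken at 0 and about 1 week of a 4-week washout.

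This rests on two assumptions: that some men arrive on androgens, as section 7.3 foresees, and that their washout begins at or after consent. Since their number is not stated, neither the size nor the direction of any effect on the results can be calculated. The correction is still worth making, because it is cheap and protects primary-outcome baselines.

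**What to change.** Add one rule to section 7.3, repeated as a footnote to the calendar in section 12:

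*For a man who needs washout, baseline FSH, LH, testosterone, estrogen, semen and questionnaires are obtained after the 4-week washout and before first dispensing. FSH, LH and estrogen are run on the second of the two required testosterone draws. Later visits are counted from first dispensing, at 4, 12, 13, 24 and 25 weeks.*

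Men who are naive or already washed out keep the current schedule.

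**Cost, for washout men only.** No post-baseline visit is added, and section 6.1 already requires both testosterone draws. The first dose comes 4 to 7 weeks later, in Week 1 + 5 = 6 to 1 + 8 = 9, plus any wait for laboratory results. The last visit moves from Week 27 to Week 6 + 25 = 31 to 9 + 25 = 34, so the 27-week duration in section 10.3 needs a note. These men also attend more often before dosing, for the post-washout blood and semen samples.

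**Wording note.** In section 3.2, relabel the two time points as study weeks 14 and 26, that is, 12 and 24 weeks on drug.

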2. HYPOTHESIS

2.1 Alternate hypothesis

Natesto™ will not change sperm count by $\pm 10\%$ from baseline.

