3.2 Secondary Efficacy Objective

Secondary outcomes will be changes in sperm count from baseline, 14 weeks ± 7 days, and 26 weeks ± 7 days after treatment, as well as monitoring for adverse effects throughout the duration of our study.

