10.4 Statistical Analysis and Power calculation

The average and standard deviation of all relevant variables and baseline characteristics, primary and secondary outcomes will be calculated.

Change in sperm count will be analyzed using the ANOVA and MANOVA. A change in $< \pm 10\%$ will be reject the null hypothesis.

LH, FSH, E and Testosterone levels will be analyzed using one-sample t-test with repeated measures throughout the study.

IIEF-EF and SF-36 questionnaires will be analyzed and compared between the groups according to Fisher's exact test in each of the endpoints. The statistical significance will be set at $P < 0.05$.

Demographic characteristics such as age and testosterone level will be compared between groups A and B using student's test. Other demographic characteristics, such as medical background and risk factors will be compared between these groups using Fisher's exact test.

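### Semen is sampled in pairs about a week apart, but the plan gives the second samples no role and does not define baseline; combining follow-up pairs would cut the within-man variance of the sperm change by up to 25%

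*Combined protocol and SAP*

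**What the plan says.** The row "Semen Analysis" in the study calendar (section 12) is marked at Visits 1, 2, 4, 5, 6 and 7, that is Weeks 1, 2, 14, 15, 26 and 27. Section 7.4 describes the main visits, "Follow-up visits will be conducted at week 14+/- 7 days and 26+/- 7 days", and then adds: "Additional semen analysis will be performed at weeks 15+/- 7 days and 27+/- 7 days". It gives no purpose for the extra samples.

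Objective 3.2 reads: "Secondary outcomes will be changes in sperm count from baseline, 14 weeks ± 7 days, and 26 weeks ± 7 days after treatment". Weeks 15 and 27 are not mentioned. Section 2.1 sets the limit, "Natesto™ will not change sperm count by $\pm 10\%$ from baseline", and section 10.4 says "Change in sperm count will be analyzed using the ANOVA and MANOVA" and rejects the null hypothesis when the change is smaller than ±10%. Section 10.1 also lists semen analysis after 6 months as a primary endpoint. None of sections 3.2, 10.1, 10.2 or 10.4 says which sample is baseline, whether two samples are combined, or what happens if one is missing.

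Two other places bear on the point. Exclusion 5 in section 6.2 applies a sperm-concentration limit to the screening semen analysis, and the calendar labels Visit 1 as screening. Section 4.2 gives a 24-week treatment course, and the calendar first dispenses drug at Visit 2 (Week 2).

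**The concern.** Two things are at stake.

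**Precision.** A ±10% limit on sperm count is tight, and a single ejaculate is a noisy measurement. Each man already gives two samples around each assessment, and nothing in the plan says that the second will sharpen the estimate.

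**Open choice.** With two candidate baselines and two candidate samples at each follow-up, a single-sample change at Week 14 or at Week 26 can be formed in 2 × 2 = 4 ways, before any form of averaging is counted. The study describes no blinding, and its success rule is whether the estimate lies within ±10%. That choice should be fixed before the data are seen.

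**Working it through.** **1. The plan's own figures.** There is nothing to reproduce. Despite its title, section 10.4 gives no SD, power or within-man variance. The sample size is 80 in sections 6.3 and 10.3 and 40 in section 4.1. I use 80 and show 40 as well.

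**2. Variance of one man's change (log scale).** Let W be the within-man variance of one sample, r the correlation of the two errors in a pair, and D the between-man variance of the true change. The documents give none of these.

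| Samples used | Variance of change | Within-man part at r = 0 | Ratio to single |
|---|---|---|---|
| Single at both ends | D + 2W | 2W | 1 |
| Single baseline, paired follow-up | D + W + W(1+r)/2 | 1.5W | 0.75 |
| Paired at both ends | D + W(1+r) | W | 0.50 |

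**3. Which row applies.** Every man is screened on the Visit 1 sample, so averaging it into baseline would bring selection, and hence regression to the mean, into the comparison. That leaves Visit 2 alone as baseline, and the second row for Week 14. At Week 26, a 24-week course started at Week 2 ends at 2 + 24 = Week 26, before Visit 7. Until the passages on treatment end are reconciled, Visit 6 stands alone and the first row applies, with no gain.

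**4. Effect on the ±10% rule.** Assume within-man log SD √W = 0.5, n = 80, r = 0, D = 0. The rule is read as: the estimated mean log change lies between ln 0.9 = −0.1054 and ln 1.1 = 0.0953.

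- Single samples: SE = 0.5 × √(2/80) = 0.0791. No true change: Φ(0.0953/0.0791) − Φ(−0.1054/0.0791) = Φ(1.206) − Φ(−1.333) = **79%**. True 20% loss (ln 0.8 = −0.2231): 1 − Φ((−0.1054 + 0.2231)/0.0791) = 1 − Φ(1.490) = **6.8%**.
- Paired follow-up: SE = 0.5 × √(1.5/80) = 0.0685. No true change: Φ(1.392) − Φ(−1.539) = **86%**. True 20% loss: 1 − Φ(1.720) = **4.3%**.
- Both ends paired (ceiling): SE = 0.5 × √(1/80) = 0.0559, giving 93% and 1.8%.

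**5. Sensitivity of the paired-follow-up case.** SD stays at 0.5.

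| Change in assumption | SE, single → paired follow-up | Pass, no change | Pass, 20% loss |
|---|---|---|---|
| r = 0.5, n = 80: 2W → 1.75W | 0.0791 → 0.0739 | 79% → 82% | 6.8% → 5.6% |
| D = W, n = 80: 3W → 2.5W | 0.0968 → 0.0884 | 70% → 74% | 11.1% → 9.1% |
| n = 40, r = 0, D = 0 | 0.1118 → 0.0968 | 63% → 70% | 14.4% → 11.1% |

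**6. Would a 90% confidence interval fit the band?** Half the band is (0.0953 + 0.1054)/2 = 0.1003. At n = 80 (t = 1.664) and SD 0.5, the half-width is 0.132 with single samples, 0.114 with paired follow-up and 0.093 with both ends paired. The first two cannot fit. In the third, the chance that the interval lies inside the band with no true change is only about 10%. Solving 0.1003 = t × s × √(f/n), where f is the multiple of W in step 2, the largest SD at which a perfectly centred interval fits moves from 0.381 to 0.440 with paired follow-up at n = 80, and from 0.266 to 0.308 at n = 40.

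**The case against.** **The plan may already use every sample.** A reader might infer that single samples will be analysed and half the data discarded. Objective 3.2 reads most naturally that way, but the documents do not say so. An ANOVA with unspecified factors could take in all six samples, and 3.2 names time points, not numbers of samples. What stands is that no rule exists.

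**Averaging might be thought to halve the variance.** That needs pairs at both ends and independent errors, and it concerns only the within-man part. The use of Visit 1 for screening removes the first condition. For men coming off androgens there is a further doubt about Visit 1: section 7.3 asks for four weeks of washout before first treatment, while the calendar puts one week between Visits 1 and 2.

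**Pairing might be thought to make the ±10% question answerable.** At an SD of 0.5 it does not, as step 6 shows. It helps, but it is no substitute for a sample-size calculation.

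**Pair members may not be interchangeable.** The ±7-day windows for Weeks 14 and 15 overlap, as do those for Weeks 26 and 27, so a one-week gap is not guaranteed. Visit 7 may be off treatment. Also, a mean of log counts is undefined at zero, and section 8.1 warns of occasional azoospermia. These objections stand and shape the fix. They limit the size of the gain, not the need for a rule.

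**Conclusion.** The point holds as an undefined rule with a cheap gain in precision. Semen is collected in three pairs, the plan assigns the second samples no role, and baseline is not identified. Combining follow-up samples cuts the within-man variance of the change by 25% at Week 14, and by the same at Week 26 only if Visit 7 proves to be on treatment; otherwise there is no gain there. Half is a ceiling that the screening use of Visit 1 rules out.

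In the worked example the pass probability moves from 79% to 86% with no change, and from 6.8% to 4.3% with a 20% loss. Those figures rest on an assumed within-man log SD of 0.5, 80 men, independent errors and no between-man variation in true change; step 5 shows smaller gains when the last two are relaxed. This should be put right, but by itself it neither invalidates nor rescues the sperm analysis.

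**What to change.** Add to section 10.4:

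> Sperm count at each time point is the mean of its two samples on [stated scale], with zero counts handled by [stated rule]. Week 14 uses Visits 4 and 5. Week 26 uses Visits 6 and 7 if both are on treatment, otherwise Visit 6 alone. Baseline is Visit 2, because Visit 1 is the screening sample used for entry. If one sample of a pair is missing, the other is used.

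Before the Week 26 line is finalised, the treatment length in section 4.2 and the dispensing and visit weeks in the calendar must be reconciled. Which is right is for the investigators to say. Because the windows overlap, the rule should also state a minimum interval between the two samples of a pair.

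An equivalent is a mixed model on the same samples, with time point as factor and man as random effect. A man-by-time-point term would keep the two samples of a pair from being treated as independent.

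The cost is a short paragraph, a decision on scale and zeros, and the reconciliation just named. No visit or sample is added. The one downside is that each follow-up time point becomes roughly a one-week average.
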